**Supporting Refugee and Immigrant Youth's Mental Health: Examining Effectiveness and Implementation of a
School-Based Intervention**

NCT05208359

02/14/2025

STRONG will be implemented in six public schools during 2021-2022 academic year and six public schools during the 2022-2023 academic year. We anticipate three elementary schools and three high schools each year. Within CPS, school leadership has requested interventions specifically designed for refugee and immigrant students due to school population and need. In each school, one group of approximately five students will be implemented. Schools will be randomly assigned to either provide the STRONG program immediately (immediate treatment) or after three months (delayed treatment). Randomization will include balancing of elementary and high schools so that the number of elementary and high schools randomized to immediate vs. delayed treatment will be equivalent. School mental health staff (e.g., district-employed social workers or community clinicians who provide services in schools) will co-facilitate groups in schools, meeting once a week. School-based clinicians are typically expected to deliver one to two small group interventions as part of their job duties. District partners have committed to supporting clinicians in delivering STRONG as part of this expectation. The research team, comprised of 10 undergraduate students and four graduate students, will collect data at baseline and then at three- and six-months post baseline. Undergraduate and graduate student pairs will meet with students and parents at schools allowing for support and mentorship of undergraduate research assistants along with clinical expertise from graduate students enrolled in the Clinical Psychology PhD program at Loyola University Chicago.

Eligibility Criteria

Students will be identified by trained STRONG clinicians consistent with standard school procedures, which include teacher and other school staff referral, parent nomination, and clinician identification from other support services. Eligibility criteria include (1) newcomer status (students who have migrated to a new country) and (2) difficulties in functioning or coping as assessed by school staff (teacher, school-based clinician). Referral reasons may include general difficulties, academic performance, peer relationships, family relationships, physical problems, behavioral concerns, and/or appearance of affect, among others. The eligibility criteria are intentionally designed to be broad (i.e., not a strict clinical cutoff) with the purpose of being more inclusive, understanding that cultural and environmental differences may produce different behavioral and emotional outcomes than what typical clinical assessments capture (Alegria et. al, 2008). In addition, researchers call for mental health treatment for refugee and immigrant children that can address trauma, acculturation, isolation, and resettlement, to better address needs (Ellis et. al, 2020). Due to the diversity in experiences, this can also impact the presenting concerns of children during the resettlement process. (Ellis et. al, 2020). Thus, it is important to have a broader inclusion criterion to best fit the needs of this group. This way children that may not be presenting with solely PTSD symptoms, including anxiety, depression, and stress management problems can also benefit from a mental health intervention that highlights their strengths. STRONG allows for this flexibility needed in addressing presenting concerns among this diverse population.

Intervention

Training for clinicians to implement STRONG will occur in fall 2021. Training will be facilitated by the Center for Childhood Resilience (CCR) at Lurie Children's Hospital. The STRONG training is two days and provides an overview of each session, practice of strategies, and implementation planning. STRONG includes 10 small group sessions, one individual session (for journey narrative), and teacher and parent education sessions. There is an elementary and high school version of the manual, modified for developmental appropriateness (Hoover et al., 2019). Group sessions include recognizing internal strengths, identifying family/social supports, relaxation, mindfulness, cognitive coping, and problem-solving. Each session includes newcomer-specific examples and support for students in applying strategies to their newcomer experience as well as natural opportunities to foster positive identity and build on strengths (Hoover et al., 2019).

In the elementary and high school groups, session one helps students identify internal strengths and external support systems (family/social supports), while in session two students learn about stress and how it impacts their bodies and minds. In the third session, stress reactions and feeling identifications are explored, and in the fourth session feelings management is discussed. In session five, students begin the session by sharing an object that represents where they are from, fostering positive cultural identity. Then, students begin to explore the cognitive aspect of mental health and learn about using helpful thoughts. In session six, children learn about the "steps to success", in which they create goals and manageable steps to achieve them, as well as ways to address avoidance. In session seven, children are taught different strategies for problem solving. In session eight, students share something meaningful from their home country (e.g., favorite food, special place, favorite tradition) and then share parts of their journey with the group. In the ninth session, students share about a favorite holiday or tradition and then continue sharing about their journeys. Then in session 10, students take turns appreciating strengths they have noticed about group members and then take part in a

graduation celebration. Between sessions four and eight, students meet individually with the clinician to discuss their journey to the U.S. This may include positive and difficult experiences, including potential traumatic experience. The clinician guides students to recognize strengths that helped them get through their journey rather than focusing on a single event with repeated retelling. The journey narrative is flexible to allow students to discuss multiple traumatic experiences, while also highlighting strengths and assets. It is recommended that the clinician screen for significant PTSD symptoms in individual sessions to consider if additional referrals will be necessary after STRONG. Clinicians also have individual sessions with caregivers and teachers to provide psychoeducation on the children's participation in the STRONG program. This allows for caregivers and teachers to support the student's progress in multiple settings (Hoover et al., 2019).

Participants

An estimated 60 students will participate in STRONG (five students per group across six public schools over two years). Student age range will be 8-18, though each STRONG group will be comprised of students within one grade level of each other. Clinicians, school personnel (teachers, administrators), and parents will be invited to complete measures and participate in focus groups (clinicians) or interviews (teachers, administrators). Teachers who have students participating in STRONG and/or assisted with referrals/identification of students will be recruited to participate in interviews. Teacher participants will be identified in collaboration with school partners/administrators. For example, English Language Learner (ELL) teachers have been key partners in referrals/identification of students in our preliminary feasibility pilot.

Procedure

Clinicians will identify eligible students and reach out to parents/caregivers consistent with standard school procedures. Clinicians will offer a group or individual information meeting to share more about STRONG and will ask parent permission to share contact information with the research team. With permission, the research team will meet with parents as part of the informational meeting or at a later date to provide additional information about the research protocol and obtain informed consent and assent.

Data will be collected from students, parents, and teachers at baseline and then at three- and six-months post baseline. Questionnaires will include measures of emotional/behavioral symptoms as well as coping and resilience. Caregivers will also be asked to provide demographic information. The three-month assessment point will represent "post-intervention" data for students at schools randomized to immediate treatment, and will be a second "pre-intervention" time-point for students at schools randomized to delayed treatment. The six-month assessment will represent three-month follow-up data for students at schools randomized to immediate treatment and "post- intervention" data for students at schools randomized to delayed treatment. School-based mental health staff will complete fidelity monitoring forms after each session, and will provide quantitative and qualitative feedback on their satisfaction with the program. Parents and students will receive a \$30 gift card for each of the three assessment they complete. After Year 1 STRONG groups conclude, clinicians will be invited to participate in focus groups, while school staff will be interviewed. Clinicians will receive \$40 gift card incentives for completion of STRONG training, completion of each STRONG group, and participation in focus groups. School staff (teachers, administrators) will receive a \$40 gift card for participation in interviews. See Table 3 for a timeline of research tasks.

Measures

Measures were selected due to availability in multiple languages (e.g., SDQ, CD-RISC). Measures not available in Arabic, Spanish, or Urdu have been forward and backward translated. See below for summary of measures. Student self-report measures are appropriate for students age 11 and older. Thus, for students ages 8-10, only parent and teacher report will be collected.

Table 3. Timeline of major research tasks.

YEAR 1: FALL		WINTER		SPRING		SUMMER
Immediate Treatment						
Training; Group formation	Consent; Randomization ; Baseline/Pre-Treatment Assessment	STRONG Group	Post-Treatment Assessment	Wait Period (No Treatment)	Repeated Post-Treatment Assessment; Focus Groups & Interviews	Data entry & scoring; Preparation for analyses

Delayed Treatment						
Training; Group formation	Consent; Randomization ; Baseline Assessment	Waitlist (No Treatment)	Repeated Baseline Assessment	STRONG Group	Post-Treatment Assessment; Focus Groups & Interviews	
YEAR 2: FALL		WINTER		SPRING		SUMMER
Immediate Treatment						
Group formation	Consent; Randomization ; Baseline/Pre-Treatment Assessment	STRONG Group	Post-Treatment Assessment	Wait Period (No Treatment)	Repeated Post-Treatment Assessment	Data entry & scoring; Preparation for analyses
Delayed Treatment						
Group formation	Consent; Randomization ; Baseline Assessment	Waitlist (No Treatment)	Repeated Baseline Assessment	STRONG Group	Post-Treatment Assessment	
YEAR 3: FALL		WINTER		SPRING		SUMMER
Finish Quantitative Analyses; Code Qualitative Data		Finish Coding Qualitative Data and Conduct Thematic Analysis; Begin preparation for publication		Share findings with partners; Plan future implementation/dissemination; Submit findings for publication; Prepare R01 grant application		

Student Mental Health. Parents, teachers, and students will complete the Strengths and Difficulties Questionnaire (SDQ), a 25-item measure that assesses mental health functioning (Goodman, 1997). It includes a Total Difficulties score and four problem subscales: hyperactivity/inattention scale (e.g., "Restless, overactive, cannot stay still for long"); the emotional symptoms scale (e.g., "Often unhappy, down-hearted or tearful"); the conduct problems scale (e.g., "Generally obedient, usually does what adults request"); the peer problems scale (e.g., "Generally liked by other children"). It also has a prosocial scale (e.g., "Considerate of other people's feelings"). Teachers will complete the SDQ based on their observations of students within their classrooms. Parents will complete the SDQ based on their observations of their child at home. Students will self-report on their mental health. Respondents rate statements on a 3-point scale from *Not true* to *Certainly true*. The SDQ is available in a number of languages including Arabic, Spanish, and Urdu.

Resilience. Students will complete the Connor-Davidson Resilience Scale (CD-RISC) pre- and post-intervention. This 25-item measure is used to assess resilience in children and strengths when facing adversity (Connor & Davidson, 2003). Example items include "I am able to adapt when changes occur," "Past successes give me confidence in dealing with new challenges and difficulties," "I tend to bounce back after illness, injury, or other hardships." Students are instructed to reference the previous month as they respond to each item on a 5-point scale from *Rarely true* to *Nearly all of the time*. The CD-RISC is also available in a number of languages including Arabic, Spanish, and Urdu.

Coping. Parents and students will complete measures of student coping efficacy (Sandler et al, 2000), which includes seven items assessing students' beliefs about their abilities to handle and cope with difficult situations. An example item is "The things people do to handle stressful problems sometimes work well to make the situation better and sometimes they don't work at all. How well do you think that the things your child does to cope work to make *situations better*?" Students respond to items using a four-point scale from *Not at all good* to *Very good*. Parents will rate student coping and responses to stress during the resettlement period in the U.S. on the Responses to Stress Questionnaire (RSQ; Connor-Smith et al., 2000). The RSQ includes subscales for primary control coping (e.g., problem solving; "She/he asks other people for help or for ideas about how to make the problem better"), secondary control coping (e.g., cognitive restructuring; "She/he thinks about the things he/she is learning from the situation, or something good that will come from it"), and disengagement coping (e.g., avoidance; "She/he tries to stay away from people and things that make her/him feel upset or remind her/him of the problem"). Parents will rate how much their child engages in each item on a

scale of 1 (*Not at all*) to 4 (*A lot*). The RSQ consistently demonstrates good reliability and validity including with Spanish-speaking populations (Connor-Smith et al., 2000). In our preliminary feasibility pilot, we worked with [name] to modify the RSQ to be specific to resettlement stress. We have also forward and backward translated the measure in Arabic and Urdu.

School Connectedness. Students will complete the School Connectedness Scale at each assessment. This 5-item scale was adapted from the Add Health study that measures students' bond towards their school (e.g., "I feel like I am part of this school"; McNeely et al., 2002; Furlong et al., 2011). Students will complete the School Climate subscale of the California Healthy Kids Survey (CHKS; WestEd, 2000) to assess school relationships and support (9 items; e.g., "At my school, there is a teacher or some other adult who really cares about me"). Students will rate the items on a rating scale from 1 (*Not at all true*) to 4 (*Very much true*).

Fidelity, & Student Engagement. Clinicians will complete a fidelity checklist for each session indicating whether core content was covered on a scale ranging from 0 (*Not at all*) to 3 (*Thoroughly covered*), with the specific items varying by session. Clinicians will additionally identify challenges, activities that were well received, and amount of time per session. Clinicians will rate students' engagement and current functioning during each session.

Satisfaction. After STRONG implementation, clinicians will respond to six items (e.g., implementation challenges, satisfaction with training) and parents will rate four items (e.g., benefits of the program, importance of the program) on a five-point scale from *Not at all* to *A whole lot*. Children will rate how much they liked the STRONG curriculum on a three-point scale from *Not at all* to *Very much*.

Analytic Strategy

Quantitative and qualitative methods will be utilized at various stages of the study. Intent to treat analyses will be conducted, and imputation approaches will be considered. Pre-treatment group differences will be included as covariates in analyses, as appropriate. Outliers and assumptions of normality will be examined and transformations considered. Consultation with [name] and [name] will include discussion of data analyses. See Figure 1 (also shown in Specific Aims) for conceptual model guiding Aims 1 & 2.

Aim 1. To test the hypotheses that students who participate in STRONG will show improvements in self-reported, parent-reported, and teacher-reported mental health (emotional symptoms, conduct problems, hyperactivity/inattention, and peer problems) as compared to the waitlist control group, repeated measures Analyses of Variance (ANOVA) will be conducted (***Aim 1, Hypothesis 1***). Repeated measures ANOVAs will be conducted on the primary mental health variables (total difficulties, emotional symptoms, conduct problems, hyperactivity/inattention, and peer problems) from baseline to post-treatment to test for a significant Time X Group interaction. Power analyses conducted with GPower (Faul et al., 2006) indicate that a sample size of N=54 is required to detect a Time X Group interaction with a medium effect using two time-points and N=44 utilizing all three repeated measures, suggesting adequate power.

Aim 2. To test the hypotheses that students who participate in STRONG will show improvements in self-reported resilience, coping efficacy, school connectedness and parent-reported coping (***Aim 2, Hypothesis 1***), repeated measures ANOVAs will be conducted on resilience, coping, and school connection from baseline to post-treatment to test for a significant Time X Group interaction. To test the hypothesis that these changes will be related to student mental health improvement/maintenance over time (***Aim 2, Hypothesis 2***), hierarchical linear modeling (HLM) will be utilized. HLM analyses (repeated measures nested within individuals) will allow for an examination of how changes over time on intervention targets (resilience, coping, and school connection) predict student mental health trajectories across all three time-points for the immediate treatment group. This approach is ideal for nested data and capitalizes on all existing time points.

Aim 3. To examine implementation of STRONG, qualitative methods will be employed. Focus group and interview scripts will be developed to assess implementation challenges and successes, as well as how the intervention fit within the school/community context and across differing newcomer pathways (e.g., refugee vs. immigrant). We prioritize focus groups with clinicians and interviews with teachers and administrators because qualitative data were not collected with these groups in our preliminary feasibility pilot (only parent and student interviews were conducted). Focus groups and interviews will be audio-recorded and transcribed. Transcripts will be imported into Dedoose, a qualitative software program designed to facilitate thematic coding. Codes will be generated using an integrated approach—determined by participant responses and informed by past literature (Bradley et al., 2007). Codes will be clarified and revised as necessary and broad themes will be identified. Responses to open-ended satisfaction questions for students and parents will also be examined for themes. Finally, fidelity ratings from clinicians will be examined along with satisfaction ratings from parents and students.

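### Table 3 lists randomization before the baseline assessment in both arms and both years, and nothing withholds allocation until baseline forms are in, so reporters can know their arm when they give baseline ratings

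*Combined protocol and SAP*

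**What the plan says.** The opening description of the study sets the unit and the arms: "Schools will be randomly assigned to either provide the STRONG program immediately (immediate treatment) or after three months (delayed treatment". It mentions balancing of elementary and high schools, but not when the draw takes place relative to baseline.

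Table 3 is the only place that gives an order. The immediate-arm rows read "Consent; Randomization ; Baseline/Pre-Treatment Assessment" and the delayed-arm rows read "Consent; Randomization ; Baseline Assessment", in Year 1 and again in Year 2.

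On who reports, the Procedure section says: "Data will be collected from students, parents, and teachers at baseline and then at three- and six-months post baseline". Under Measures, for the mental health outcome: "Parents, teachers, and students will complete the Strengths and Difficulties Questionnaire (SDQ), a 25-item measure that assesses mental health functioning". Coping is rated by parents and students, and resilience and school connectedness by students only. Children aged 8 to 10 give no self-report. On who collects the data: "Undergraduate and graduate student pairs will meet with students and parents at schools".

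Under Analytic Strategy, Aim 1 and Aim 2 Hypothesis 1 both use repeated measures ANOVA "from baseline to post-treatment to test for a significant Time X Group interaction". The same section adds: "Pre-treatment group differences will be included as covariates in analyses, as appropriate".

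**The concern.** Baseline should be measured before allocation can influence it. Here everyone in a school shares one allocation, the difference between arms is openly the start date, and school clinicians both recruit families and run the groups. Once a school has its slot, the news can easily reach parents, students and teachers before they fill in the first questionnaires.

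All effectiveness outcomes are subjective ratings, and the baseline rating is half of the contrast being tested. Reporters at a waitlisted school might stress need, and reporters at a school about to start might already be hopeful. Either would make the arms differ at baseline for a reason unrelated to the students' condition, and the Time X Group term would take up part or all of that difference. Open follow-up ratings are hard to avoid in a waitlist design. Open baseline ratings are avoidable.

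**Working it through.** **1. Order of tasks.** The four rows of Table 3 (immediate and delayed, Years 1 and 2) agree: consent, randomization, baseline. The three tasks share one cell, so the order rests on how they are listed. Other multi-task cells read chronologically (training before group formation; data entry before preparation for analyses). No section gives a different order, and none mentions blinding, concealment or delayed disclosure.

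**2. The plan's own figure.** Aim 1 states N=54 for two time-points and N=44 for three, for a medium effect. Effect size f, alpha, power and within-person correlation are not given, so I assume f = 0.25, alpha = 0.05, rho = 0.5 and sphericity. For m time-points, lambda = f² × N × m / (1 − rho), with df 1 = m − 1 and df 2 = (N − 2)(m − 1).

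- m = 2, N = 54: lambda = 0.0625 × 54 × 2 / 0.5 = 13.5; power 0.950.
- m = 3, N = 44: lambda = 0.0625 × 44 × 3 / 0.5 = 16.5; power 0.956.

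Both stated sizes are reproduced at a power target of 0.95. They do not depend on the order of randomization and baseline.

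**3. How a baseline shift enters the test.** Let b0 be the between-arm difference (immediate minus delayed) in mean rating at baseline caused by knowing the allocation, and b3 the same at three months, in SD units. The interaction estimates the true effect + b3 − b0. If the shift has gone by three months (b3 = 0), the bias is the full −b0. If it persists unchanged (b3 = b0), it cancels. Partial persistence falls between.

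**4. Illustration.** Assumed, not from the documents: size of b0, rho, b3 = 0, no clustering, no true effect. From the plan: N = 60, taken as 30 per arm. The SD of change is √(2(1 − rho)), so the noncentrality is |b0| / (√(2(1 − rho)) × √(2/30)), with 58 df and a two-sided 5% test. For b0 of size 0.2 and rho = 0.5: 0.2 / (1 × 0.258) = 0.775.

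| Shift (SD) | Rejects, rho 0.5 | In the direction of the bias | In the opposite direction | Rejects, rho 0.7 |
|---|---|---|---|---|
| 0.1 | 6.7% | 5.7% | 1.0% | 7.8% |
| 0.2 | 11.9% | 11.5% | 0.3% | 16.6% |
| 0.3 | 20.8% | 20.7% | 0.1% | 31.4% |

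**5. Direction.** Suppose waitlist reporters stress need, or immediate-arm reporters are hopeful, at baseline only. Baseline difficulties are then higher in the delayed arm, and that arm appears to improve more. False rejections favouring the waitlist become 5.7%, 11.5% and 20.7%, and false rejections favouring STRONG fall from the nominal 2.5% to 1.0%, 0.3% and 0.1%. A real benefit is also hidden: a true 0.5 SD difference in change, less a 0.2 SD shift, appears as 0.3 SD, and power falls from 48% to 21% (rho = 0.5). The opposite baseline shift would overstate benefit by the same mechanism.

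**The case against.** The strongest reply is that a listing inside one cell of a timeline is thin evidence, and that the plan never says when anyone is told the result of the draw. That stands in part. A reader might infer that reporters will know their arm, or that they are declared unblinded. The documents say neither; they support only that reporters can know. Consent is listed before randomization, so the table does not show recruitment after allocation either.

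Three other strong readings fail.

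- A reader might take the rejection rates above as inflated false claims of benefit. Under the most natural mechanism they run against STRONG, and nothing in the plan fixes the direction.
- A reader might treat the bias as always equal to the shift. At three months the delayed arm is still waiting, so the motive to stress need may persist and part of the shift may cancel. Full size is the upper case.
- A reader might conclude that the covariate sentence adjusts for baseline outcome scores already distorted by allocation. It does not name those scores, and the covariates could be demographics. The sentence is no evidence of a further fault, although it offers no safeguard.

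The shift sizes and the correlation have no source in the documents, so the table shows sensitivity, not an expected error rate. What survives is that the only stated sequence permits an avoidable bias and that no safeguard is written down.

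**Conclusion.** The point holds as a risk in the stated sequence, not as a demonstrated bias. The only order the plan gives puts allocation before baseline, every outcome in the between-group tests is a subjective rating, and those tests depend directly on the baseline score. A shift caused by knowing the allocation would bias the interaction by between nothing (equal persistence at three months) and its full size (no persistence), in an unknown direction. With assumed shifts of 0.1 to 0.3 SD and no persistence, two-sided rejection under no true effect is 6.7% to 20.8% at rho = 0.5 and 7.8% to 31.4% at rho = 0.7, ignoring clustering by school. The change is a cheap improvement and worth making. It does not address knowledge of allocation at follow-up, which is a separate matter.

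**What to change.** Change Table 3, in both arms and both years, to the order consent, baseline assessment, randomization. If schools must be drawn earlier for scheduling, have someone already on the team but outside data collection hold the allocation, and release it to a school, its families and the assessors only after that school's baseline forms are collected. State the chosen rule in the Procedure section. If allocation is already withheld in practice, one sentence saying so settles the point.

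For cohorts already assessed, report the actual order and when allocation was disclosed to schools, families and assessors.

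Cost: no extra students, staff, visits or measures. Schools learn their start slot later. Because the draw is balanced across elementary and high schools, drawing all schools after baseline may mean waiting for the slowest one; the held-allocation option avoids that.

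### Intent to treat is promised but no missing-data method is fixed, and the unadjusted repeated measures ANOVA uses completers by default, loses precision, and is biased if dropout depends on baseline differently by arm

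*Combined protocol and SAP*

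**What the plan says.** The Analytic Strategy opens with the analysis set and the handling of missing data in one sentence: "Intent to treat analyses will be conducted, and imputation approaches will be considered". It gives no imputation method, no trigger for using one and no assumption about why data are missing. It also says that group differences before treatment will enter as covariates where appropriate, which is not a commitment to adjust for the baseline score.

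For Aim 1, "Repeated measures ANOVAs will be conducted on the primary mental health variables", and the test runs "from baseline to post-treatment to test for a significant Time X Group interaction". For Aim 2 Hypothesis 1, "repeated measures ANOVAs will be conducted on resilience, coping, and school connection from baseline to post-treatment", with the same interaction test. For Aim 2 Hypothesis 2 the plan uses hierarchical linear modelling within the immediate treatment group and says of it: "This approach is ideal for nested data and capitalizes on all existing time points".

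The Procedure section sets assessments at baseline, three months and six months, from students, parents and teachers. The three-month visit is post-intervention for the immediate arm and a second pre-intervention visit for the delayed arm. The comparison with the waitlist is therefore read here as baseline to month 3. On size, the Participants section says "An estimated 60 students will participate in STRONG", and Aim 1 says that "a sample size of N=54 is required to detect a Time X Group interaction with a medium effect using two time-points". No dropout rate or attrition allowance is stated.

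**The concern.** Standard repeated measures ANOVA needs a complete set of the waves it uses. A randomised student whose parent form is missing at month 3 drops out of the parent-report test unless something is imputed, and the plan leaves open whether anything will be. The choice between completers and imputed data would then be made after the data are seen, across three informants and five Strengths and Difficulties Questionnaire (SDQ) outcomes.

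Missing forms are plausible: there are three informants and three visits, and one arm waits three months without treatment, so the reasons for leaving could differ between arms.

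The second issue is the estimator. An unadjusted change score makes poor use of the baseline, and among completers it picks up regression to the mean if the arms lose different kinds of students. At stake are the precision of the main comparison and, under differential dropout, a spurious benefit or a masked one.

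**Working it through.** **The plan's own sample size.** Inputs from the plan: two groups, two or three waves, a medium effect, N = 54 and N = 44. Assumed, because not stated: f = 0.25, correlation ρ = 0.5, two-sided alpha 0.05, power 0.95. Of the combinations tried (power 0.80, 0.90, 0.95; ρ 0.3, 0.5, 0.7), only this one returns both figures. Noncentrality is λ = f²·N·m/(1−ρ), with df = (m−1) and (N−2)(m−1).
- Two waves, N = 54: λ = 0.0625 × 54 × 2 / 0.5 = 13.5, power 0.950.
- Three waves, N = 44: λ = 0.0625 × 44 × 3 / 0.5 = 16.5, power 0.956.

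Both reproduce. They ignore clustering by school.

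**Completers in a two-wave test.** The loss rate q is an assumption; retained N = 60(1−q).

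| q | Completers | Two-wave power on the inputs above |
|---|---|---|
| 0% | 60 | 96.8% |
| 10% | 54 | 95.0% |
| 15% | 51 | 93.8% |
| 20% | 48 | 92.4% |
| 40% | 36 | 83.0% |

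**Precision.** With two waves, the Time X Group interaction is the difference between arms in mean change. For standardised scores the change has variance 2(1−ρ); the month-3 score adjusted for baseline has variance 1−ρ². The ratio is (1−ρ²)/(2(1−ρ)) = (1+ρ)/2:
- ρ = 0.3: 0.65
- ρ = 0.5: 0.75, so 25% lower with adjustment
- ρ = 0.7: 0.85

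This holds with no missing data at all.

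**Bias, constant effect, dropout depending on baseline.** With equal means over time before any effect, the expected error in one arm's mean change is −(1−ρ) × (mean standardised baseline of its completers). Assume 15% dropout with log-odds rising by 1 per SD of baseline symptoms. Numerical integration gives completers a mean baseline of −0.133 SD. At ρ = 0.5 that arm's change is off by 0.5 × 0.133 = 0.066 SD. The contrast is immediate minus delayed, and negative favours treatment:
- Same slope in both arms: 0.066 − 0.066 = 0.
- Delayed arm only: 0 − 0.066 = about −0.07 SD.
- Opposite slopes (better-off students leave the immediate arm, worse-off the delayed arm): −0.066 − 0.066 = about −0.13 SD.

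At ρ = 0.7 the last two become 0.3 × 0.133 = 0.04 and 0.08 SD. At ρ = 0.5 and 20–24% loss, large-sample simulation gives 0.10 SD (dependence in one arm only) and 0.20 SD (opposite slopes).

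**Simulation at trial size** (no true effect, 30 per arm, ρ = 0.5, 15% dropout, slope 1, 20,000 trials, no school clustering):

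| Dropout pattern | Change-score bias | Error rate | Baseline-adjusted bias | Error rate |
|---|---|---|---|---|
| Same slope in both arms | 0.00 | about 5% | 0.00 | about 5% |
| Delayed arm only | −0.07 SD | about 6% | 0.00 | about 5% |
| Opposite slopes | −0.13 SD | about 7.5% | 0.00 | about 5% |

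The adjusted analysis was run on the same completers, and its variance was about a fifth to a quarter lower.

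**Link to the mixed model.** With two waves, every baseline observed and no school term, a likelihood with a common baseline mean splits into a baseline part and a part for month 3 given baseline and arm. The month-3 contrast is then the arm coefficient from the baseline-adjusted regression, so the adjusted results carry over. Beyond that, the mixed model also uses students who have month 3 but no baseline form, or month 6 but no month 3.

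**The case against.** The best defence is that the plan is incomplete rather than wrong. The sentence that promises intent to treat also allows imputation, and an ANOVA on imputed data would include every randomised student. This stands. A reader might infer that the named method contradicts intent to treat; the documents show only that the method does not secure it.

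Three further limits also stand.
- A reader might infer that any missed visit removes a student. The named tests run from baseline to post-treatment, so a student who misses only month 6 stays in the month-3 comparison. A missing form affects only that informant's analysis, and the hierarchical model can keep partial data.
- A reader might infer that dropout related to baseline symptoms biases the result in general. It biases change within an arm. With a constant effect, the tested contrast is biased only if the relation differs by arm.
- A reader might set completers across three waves against "N=44 utilizing all three repeated measures, suggesting adequate power" and conclude that power fails. The named tests use two waves, and 48 completers still give about 92% power on the inputs that reproduce the plan's figures. Lost power is not the main issue.

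It is also fair to say that the demonstrated gain comes from baseline adjustment, not from keeping more students, and that the plan's covariate sentence could allow such adjustment. But that sentence is conditional and concerns group differences before treatment. It commits to adjusting for the baseline score no more than imputation is committed.

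**Conclusion.** The point holds in this form: the plan promises intent to treat, fixes no missing-data method, and uses an unadjusted change-score test that runs on each informant's completers by default. The loss of precision needs no dropout: adjustment would lower the variance by about 25% at ρ = 0.5 (35% at 0.3, 15% at 0.7). The bias is conditional and modest: none with equal dependence on baseline in both arms, about 0.07 SD with dependence in the delayed arm only, and about 0.13 SD with opposite directions.

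The bias figures rest on assumptions that the documents do not give: 15% dropout, a log-odds slope of 1 per SD, ρ = 0.5, a constant effect and no school clustering. Baseline adjustment does not cure everything. If the effect grows by 0.2 SD per SD of baseline and worse-off students leave both arms (slope 1, about 24% loss), both the change-score and the adjusted contrast give −0.46 SD instead of −0.50. These calculations do not cover dropout that depends on the unseen month-3 score. The change should be made because it is better even with complete data and costs little.

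**What to change.** Replace the repeated measures ANOVAs for Aim 1 and Aim 2 Hypothesis 1 with a linear mixed model fitted by REML to all randomised students with at least one assessment, separately for each informant and outcome. Specify time as a category, a common baseline mean for both arms, group-by-time terms, and random effects for student and school. Name the month-3 group contrast as the test. Use multiple imputation as a sensitivity analysis, with its method stated in advance. Report the number of students with data by arm, informant and visit; students aged 8–10 have no self-report by design and should be shown separately from missing forms.

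The cost is analysis wording and slightly more modelling. No new data are needed, and the method is close to the hierarchical model already planned for Aim 2 Hypothesis 2.
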